Several studies have shown that unmet needs regarding physical and psychosocial problems are frequent and diverse among cancer patients. Furthermore, care gaps regarding treatment of comorbidities are substantial.¹⁵⁻¹⁸ The general practitioners (GPs) have been given a central role as coordinators of the cancer patients' course. However, supporting cancer patients with regard to rehabilitation needs still poses a huge challenge for GPs during and following long-term hospital-based cancer treatment.¹⁹⁻²¹

A Danish study from about unmet needs of rehabilitation of 3,439 cancer patients demonstrated that a total of 60% expressed unmet needs in at least one of six different areas: physical, emotional, family-oriented, sexual, work-related and financial.^{16 22} Unmet needs in several areas were common.²² Unmet needs with regard to physical and emotional support were most common.²² Furthermore, the authors found that unmet needs were associated with lower quality of life according to EORTC QLQ C-30, thereby showing that unmet needs and reduced quality of life are correlated.²² From the time of diagnosis to long after the treatment and the regular contact to the hospital are completed, needs for rehabilitation occurs and often changes during the cancer trajectory.^{21 23} This supports the fact that GPs should play a central role in rehabilitation early in the treatment.²⁴⁻²⁷ However, a Danish survey of 4,401 cancer patients two years after diagnosis showed that 21.7% of the participants had apparently not retrieved sufficient information about how their GP could provide support, and 30.7 to 59.8% had not retrieved adequate help from their GP regarding cancer-related physical, emotional and social problems.¹⁸ Furthermore, 42 % of patients have one or more comorbidity but only 42 % found that the hospital had handled it well.¹⁸

Continuity of care is expected to have a vital impact on the quality of care that patients receive. Interventions focusing on care gaps of continuity may improve patients' outcomes.²⁸ Furthermore, increased experienced continuity of care may be associated with lower health care needs in the future.²⁹ A Canadian survey on continuity of care found that over 55.2% of the patients did not feel they had been informed about patient resources and supports to help consolidate continuity of care.³⁰ Within the Danish healthcare setting, three large-scaled ambitious clinical cancer trials tried to improve shared decision-making, continuity of cancer care and rehabilitation across healthcare sectors. The concepts consisted of a shared-care programme, an intensive hospital-based case management programme, and a rehabilitation

programme and were headed by Nielsen, Wulff and Bergholdt, respectively.^{27 31 32} Despite rigorous designs these studies did not succeed to point out effective solutions. In Canada and Holland focus has been on the so-called survivorship care plans, but a rigorous randomised controlled trial including Canadian patients with breast cancer did not show the hypothesised effects.³³

Patient information is an essential factor in the support for cancer survivors across the whole cancer trajectory.^{34 35} Providing patients with appropriate information about their services through informed decision-making may result in lower levels of distress, improved satisfaction with care and enhanced health-related quality of life.³⁵⁻³⁷ There is still a substantial gap between patients' and families' wishes about the level of information they want to obtain, and how they want to receive it, and their satisfaction with what they really get.^{18 38}

Bringing the oncologist and GP together face-to-face with the patient in focus may improve communication between the primary and secondary sector, enhance patient involvement, improve continuity of care and thereby provide relief to cancer patients and their overall treatment results. Due to geographical reasons and shortage of time this is impossible as part of routine cancer care. Video-based communication may therefore be an alternative solution.³⁹⁻⁴⁴ Video consultations connect physicians and patients located at different places and enable them to actively share knowledge, decision-making and treatment planning. Seeing each other is important for both the doctor-patient and the doctor-doctor relationship.^{41 45 46} It gives access to rich non-verbal emotional signals and enhances the building of empathy between participants sitting apart.

In this study a new and innovative model of communication and shared decision-making will be developed and evaluated in a rigorous, randomised controlled trial. A video consultation at the start of chemotherapy including the cancer patient, the GP and the oncologist constitutes the core of the intervention. This study intervention thereby aims to support the delivery of continuity and coordinated, shared care of general as well as cancer-related health problems among cancer patients treated with chemotherapy.

Study aims

Further research based on innovative ideas is required to improve the cancer healthcare trajectory, with a conceptual idea of improving cancer care based on doctors' partnership in a patient-centred context. The aim of the study is, to design and evaluate a new way of communication and shared decision-making that brings the patient, the oncologist and GP together in a shared video consultation. A multi-modal intervention will be evaluated in a randomised controlled trial through a retrospective design.

Specific aims of the intervention will include

- 1) To reach agreement upon sharing or transfer of care between oncologist and GP during and following cancer treatment with chemotherapy.
- 2) To improve patient-perceived continuity of care by reinforcing information, management and relations among participants involved in the patients' treatment.
- 3) To reduce cancer patients' unmet needs of rehabilitation during and following chemotherapy.
- 4) To increase quality of life and reduce illness intrusiveness for cancer patients during and following chemotherapy.

Material and methods

A randomised controlled trial including 340 cancer patients referred to chemotherapy at Department of Oncology, Vejle Hospital. The included cancer patients will test the effect of this multimodal intervention aiming to enhance patient involvement, shared decision-making and sharing or transfer of care between oncologists and GPs. The effect of the intervention in addition to traditionally organised care will be compared with regard to result and process outcomes. Data will be obtained from registers and questionnaires to patients, GPs and oncologists.

Setting

Patients will be recruited at the Department of Oncology, Vejle Hospital, at their first appointment for chemotherapy. In 2013 The Department had 1.200 referrals and started chemotherapy. The five most frequent diagnoses were breast, gastrointestinal, pulmonary, gynaecological, and urinary cancer. During the inclusion period all adult patients referred for chemotherapy will be invited for the study regardless of cancer type.

Inclusion criteria

- Newly referred cancer patient scheduled for chemotherapy at the Department for Oncology, Vejle Hospital
- Aged 18 years and over
- Expected survival of median 7 month
- Able to speak and read Danish
- Mentally able to cooperate
- Listed with a GP
- Written and verbal informed consent given

Intervention

The final design of the study intervention will be based upon experience from the feasibility period. Apart from the video consultation this multi-modal intervention will include, advice on effective communication, preparation and management of the meeting, expected topics for the meeting, advice on active patient involvement, practical issues, E-learning programs, etc. ^{31 39-42 44 47 48}

The core element of the intervention consists of a video consultation, which unifies the cancer patient, the GP and the oncologist in the early phase of cancer chemotherapy treatment, thereby facilitating a powerful partnership. The video consultation is expected to last 10-25 minutes. One or more video consultations may be planned during or at the end of treatment. A project nurse will schedule the consultation. The patient may sit with the oncologist or the GP depending on the patient' request. The footage of the consultation will be available for patients to watch at home. The consultation is expected to facilitate that individual needs are timely addressed during and after treatment.

Randomisation

During a 12 to 18 months period of inclusion, all adults referred for chemotherapy will be invited for the study. Oral and written information are given at first appointment. Randomisation takes place after a baseline questionnaire and the written informed consent has been completed.

Patients are allocated to the intervention and control group, respectively, in a 1:1 ratio. Subsequently, the general practitioner is invited for the consultation. Both GPs and oncologist may thus have patients in the

control as well as the intervention group. No significant spillover effects between groups at the physicians level are expected.

The software program RedCap® will manage all handling of the questionnaire data, which is capable of automatically sending out by mail secured links to participants and retrieving answers online. The randomisation will be computer-generated by RedCap®.

The sample size of at least 214 (107 in the intervention and control group, respectively) subjects should ensure a well-balanced design. No strong evidence regarding relevant stratification factors for this type of outcome is available. Thus, the randomisation will not be stratified. However, in exploratory analysis the influence of additional factors such as: age, gender, education and cancer type will be investigated.

IT equipment and security

The requirements of video conferencing equipment should be as easily available, flexible and acceptable as possible.^{39 44} Since GPs are faced with a variety of IT communication options, an individual solution that is simple and easy to activate, should be provided. The oncologists at Vejle Hospital share consultation rooms and change location during a workday, and equipment for their disposal should be portable and easy to set-up. The project group therefore intends to use an already existing video conferencing system the Tandberg E20, which is used for video translation at hospitals and in some general practice in the Region of Southern Denmark. Those general practice how do not have the conference system will be offered a free set up and support by Syddansk Sundhedsinnovation. For does general practice how don't want the conference system a second solution call Jabber Guest is offered.

The video consultation will be stored on the Region of Southern Denmark's servers and will be available to the patient on a website with a secure login.

Outcomes

Data will be retrieved from registers and Internet-based questionnaires to patients at baseline and after 4 and 7 months and to GPs and oncologists at 4 months. All handling of the questionnaires will be managed using the software program RedCap®. The initial part of the questionnaire at baseline will include demographic and clinical information like age, cancer type, cancer recurrence status, and completion of previous chemotherapy treatment.

The primary study outcome is the total score of the decision self-efficacy scale for patients at 7 month⁴⁹. This 11-item questionnaire has previously been translated from English to Danish and used in a Danish, mixed oncology setting⁸.

The global score of the quality of life questionnaire EORTC QLQ C-30 is very often the choice of primary outcome in psychosocial cancer clinical trials. However, to target the core of the intervention as precise as possible we have selected self-efficacy of decision-making, i.e. the total scores of the cancer specific patient questionnaire Decision self-efficacy (decision-SE)⁴⁹. It assesses confidence in one's ability to participate in decision making to the extent desired. It is suggested that this measure clearly trump the global score of the EORTC QLQ-C30 with regard to our study intervention. This 11-item questionnaire has previously been translated from English to Danish and used in a Danish, mixed oncology setting⁸.

Secondary outcomes covering patients perspectives will include the following questionnaires: Global Health Status of the EORTC QLQ C-30 subscales and single items of the EORTC QOL C-30 which has high validity, knowledge from reference populations and strong correlation to unmet needs of rehabilitation.^{15 22 31 50-53}, Cancer Care Coordination questionnaire (CCCQ) assessing the patient perception of the coordination of

their cancer care in 22 items⁵⁴, The Illness Intrusiveness Rating Scale (IIRS) assessing the extent to which an illness or its treatment is viewed as interfering with different aspects of an individual's life^{55 56}, and EORTC QLQ INFO 25³⁷ covering several aspects of patient information during cancer treatment, and The hospital depression and anxiety score (HADS) assessing patient depression and anxiety symptoms. Additionally, health-seeking behaviour to the general practitioner and the oncologic department (contact form, date and aim) will be asked about.

Patients in the intervention group will additionally evaluate the content, form, expectation and experience of the video consultation. This is achieved by presenting them to ad hoc items inspired among others by the work of the Australian College of Rural & Remote Medicine.⁵⁷

In addition to patients' evaluation of health, health-seeking behaviour and the care given, evaluations from the GPs and the oncologists primarily responsible for their treatment are included as secondary outcomes. Until now, we are not aware of appropriate validated scales and therefore ad hoc item will be formulated to cover perceived benefit of the video-consultation, subsequent influence on care and coordination, satisfaction with own care, relevance of patient contacts, comorbidity care and adherence to cancer care.

Data from registers will include the National Patient Register and the National Health Insurance Register (Statistics Denmark). Furthermore, the footage of the consultations, which contributes with an important data source, will be analysed qualitatively regarding content, communication, roles etc., but this is beyond the scope of my PhD study.

Sample size calculation

Knowledge obtained from a previous study on decision self-efficacy in a mixed Danish oncology setting includes normal distribution of data with a mean of 36 and a standard deviation of 9⁸, meaning that data from 107 patients in each group allows detection of a 4 point difference with 90 % statistical power at an significance level of 0.05. Under the assumption of a high initial acceptance by general practitioners to support the individual patient's study participation (expected to be 90 % but will be proved by piloting), and patient dropout up to 30 % during follow-up (based on a prior RCT in the same setting³¹), it is planned to recruit 340 patients i.e. 170 patients in the control and the intervention group, respectively.

Design phase and pilot testing

The intervention will be pilot tested by inclusion of 10 to 15 patients and their health professionals, and adjusted accordingly. Observations will include expectations by patients, relatives, and professionals, study acceptance, study material, feasibility of the video consultations, and perceived usefulness.

Analyses

The effectiveness of this intervention will primarily be analysed based on the intention-to-treat principle, where data from all participants', having at least one post-baseline measurement of the primary outcome will be included in the data analysis.

Standard descriptive statistics will be used to report demographics, clinical characteristics and baseline status for the different outcomes.

Analysis of differences between outcome means at follow-up between the intervention and control group will be by linear regression, adjusted for baseline value of the outcome.

Statistical program Stata® version 13 will be used for data analyses.

Publications

A PhD Thesis entitled The PARTNERSHIP CANCER STUDY will be based on four papers with the following working titles:

Papers

- 1) Reinforcing partnership between cancer patient, general practitioner and oncologist during chemotherapy – study protocol for a randomised controlled trial
- 2) Patient perceived quality of life, continuity of care and unmet needs after a multimodal intervention bringing cancer patient, general practitioner and oncologist together during chemotherapy – a randomised controlled study
- 3) Sharing of medical responsibility and obtained knowledge from a General Practitioners point of view during a video consultation bringing cancer patient, general practitioner and oncologist together – results from a randomised controlled study
- 4) Benefits for Oncologist bringing cancer patient, general practitioner and oncologist together in a video consultation – results from a randomised controlled study

Perspectives

The study will add a new dimension to the organisation of cancer treatment and may be useful in other phases of cancer treatment. The intervention furthermore includes room for professional learning and sharing of knowledge. Although the study intervention is not logistically simple, it's suggested, that it can be implemented in routine cancer care. Data for qualitative analysis and economic evaluation is sampled during the trial period and will provide further knowledge important for implementation.

Budget

The overall budget of the project period 2014-2017 is estimated to be DKK 4.924.628, which covers PhD salary, salary for senior researchers including statistical assistance, running expenses, tuition fee and conference and travel expenses.

Ethics

The Regional Ethics Committee on Biomedical Research and the Danish Data Protection Agency are asked to approve the study, which will also be indexed at www.clinicaltrials.gov. All participants will receive oral and written information about the study, and participation requires written informed consent. All aspects of the study will be conducted in accordance with national and international standards and laws. It should be underlined that there will be specific focus on safety regarding the video conferencing and patient access to footage.

One may expect that some patients might bring up subjects in confidentiality with a given health care provider, which they have not discussed with other health care providers, for instance alcohol consumption. Both GPs and oncologist should be aware of this. The study material and consultation guidelines will include a note about it.

The study will be described and reported in accordance with the CONSORT statement.⁴⁸

Time schedule

01.09.2014 – 01.09.2015: Preparation of information material for patients and health staff. Apply authorisation from Danish Data Protection Agency, Danish Health and Medicines Authority, and the regional ethic committee. The feasibility of the study intervention will be analysed by inclusion of 10 to 15 patients and their health professionals in a pilot study. The different element of the intervention, inclusion procedures, study material, logistics and questionnaires are analysed.

01.09.2015 – 01.09.2016: Inclusion of patients for the randomised controlled trial.

01.09.2016 – 01.12.2017: Follow-up 7 month, analysis, result procurement and preparation of manuscripts.

Organisation

This study will be developed and conducted in a research group including supervisors and collaborators: [name] [name], PhD health economist [name] and senior statistician [name], Research Unit of General Practice, University of Southern Denmark, [name] [name], Department of Psychology, University of Southern Denmark; “Doctors Partnership” an innovative quality development group established and headed by Hospital [name], [name], Vejle Hospital, who launched the overall idea of the project, and furthermore the patient and relative Council, Vejle Hospital.

The applicant, MD [name], will be head of the PhD research project.

References

1. Kræftens Bekæmpelse. Strategisk oplæg om kræftrehabilitering: Kræftens bekæmpelse, 2010:19.

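### The intention-to-treat set includes patients with only a 4-month score, but the stated 7-month regression cannot use them, so the primary analysis is in effect complete-case

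*Protocol*

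**What the plan says.** The Outcomes section of the protocol fixes the endpoint in time: "The primary study outcome is the total score of the decision self-efficacy scale for patients at 7 month". The same section schedules "Internet-based questionnaires to patients at baseline and after 4 and 7 months", which gives two post-baseline occasions.

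The Analyses section follows the intention-to-treat principle and limits the set to participants "having at least one post-baseline measurement of the primary outcome will be included in the data analysis". It names one model, stating that "differences between outcome means at follow-up between the intervention and control group will be by linear regression, adjusted for baseline value of the outcome". It does not say which visit is meant by follow-up. The protocol names no repeated-measures model, imputation method or other rule for a missing 7-month score.

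The Sample size calculation section allows for "patient dropout up to 30 % during follow-up" and plans 340 patients, 170 per arm.

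**The concern.** An inclusion rule of at least one post-baseline score belongs to a longitudinal analysis, in which any visit contributes. The plan pairs it with a regression that needs one particular visit. For a patient seen at 4 months but not at 7, the two sentences disagree: the first includes the patient, and the second has nothing to regress.

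Two things are at stake. First, the report would describe a set larger than the one that produced the primary estimate. Second, the regression discards the 4-month score, which is likely to be informative both about who drops out and about the missing value. If dropout before month 7 depends on that score, a regression on 7-month completers can be biased, whereas a model using both visits is protected as long as the data are missing at random.

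**Working it through.** **1. The plan's own figures.** Inputs from the Sample size calculation section: difference 4, SD 9, power 90%, significance level 0.05 (two-sided, since one-sided would give 87 per arm).

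- n per arm = 2 × SD² × (z₀.₉₇₅ + z₀.₉₀)² / difference² = 2 × 81 × (1.960 + 1.282)² / 16 = 106.4, rounded up to 107. This reproduces.
- Inflation for 30% dropout and 90% GP acceptance: 107 / (0.70 × 0.90) = 169.8, so 170 per arm and 340 in total. This reproduces.

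**2. Patients with a 7-month score.** 340 × 0.70 = 238, or 119 per arm; 102 have none. Power with 119 per arm is 92.9%. If GP non-acceptance also removes patients, 340 × 0.90 × 0.70 = 214.2 remain, or 107 per arm, with 90.2% power.

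**3. Size of the mismatch.** The protocol does not say how many dropouts will have answered at 4 months. Let s be that share (an assumption). Patients in the set without a 7-month score = 102 × s; set size = 238 + 102 × s.

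| s | In set, no 7-month score | Set size | Share of set |
|---|---|---|---|
| 25% | 26 | 264 | 9.7% |
| 50% | 51 | 289 | 17.6% |
| 75% | 77 | 315 | 24.3% |
| 100% | 102 | 340 | 30.0% |

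The regression uses 238 patients in every row. One simulated data set built to the 50% row confirmed this: 289 met the inclusion rule and the fitted model used 238.

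**4. Effect on the estimate.** All of the following are assumptions: SD 9; 170 per arm; correlations 0.5 (baseline and 4 months), 0.45 (baseline and 7 months) and 0.65 (4 and 7 months); 15% lost before month 4 and 17.65% of the remainder lost before month 7, since 0.85 × (1 − 0.1765) = 0.70. The true effect is 4 at both visits. Late dropout is logistic in the 4-month score, with low scorers leaving more often.

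| Late dropout | 7-month completer regression | Bias |
|---|---|---|
| Completely at random | unbiased | none |
| Both arms, log-odds 0.5 per SD | 3.95 | about 0.1 |
| Both arms, log-odds 1 per SD | 3.8 | about 0.2 |
| Control arm only, log-odds 1 per SD | 3.3 to 3.4 | 0.6 to 0.7 |

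A likelihood estimate using both visits gave 4.0 throughout. In these scenarios the completer bias is towards a smaller effect. With no true effect and control-arm-only dependence, the completer test rejected about 10% to 11% of the time instead of 5%. The last row grows with the assumed slope: at 0.15 and 0.20 log-odds per point (1.35 and 1.8 per SD) the completer estimate fell to 3.2 and 2.9.

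**5. Precision under random dropout.** The partial correlation of the 4- and 7-month scores given baseline is (0.65 − 0.5 × 0.45) / √(0.75 × 0.7975) = 0.55, with square 0.30. The variance ratio, both visits against completers, is about 1 − 0.30 × (1 − 0.70/0.85) = 0.947. The standard error falls by about 2.7%, in line with the simulated 2-3%.

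**The case against.** **The wording allows another reading.** The regression sentence covers all outcomes and does not name a visit. A patient with only a 4-month score could be in the set and appear only in the 4-month comparison. That is a fair reading of the set, but it leaves the primary 7-month comparison with completers alone. If the inclusion rule is instead read as meaning the 7-month score, the conflict goes away, but at least one then has no function and the set is openly complete cases.

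**Missing-data handling is often left to the SAP.** This is true, and the absence of an imputation method is not the point here. The point is that the protocol's set and its only model do not fit each other.

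**A reader might infer that the 4-month score will be carried forward,** or that dropping and carrying forward are the only ways to satisfy both sentences. The protocol does not support either inference. It mentions no carry-forward, and imputing the 7-month score before running the stated regression would satisfy both sentences.

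**A reader might infer that dropout will differ by arm and that the primary result will be clearly biased.** The protocol gives only one overall dropout figure. The larger bias needs score-dependent dropout confined to the control arm; with the same dependence in both arms the bias is small. This objection stands and limits the severity.

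**The trial is not underpowered by this.** Recruitment was inflated for the planned loss. This also stands.

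**Conclusion.** The inconsistency is real and concerns the primary analysis: as written, it is a 7-month complete-case analysis under an intention-to-treat label, and it leaves a collected and useful measurement unused. The number affected cannot be derived from the protocol; it is 26 to 102 patients if 25% to 100% of the dropouts answered at 4 months.

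The harm to the estimate depends on the dropout mechanism. It is nil under random dropout, about 0.1 to 0.2 points under the same score dependence in both arms, and about 0.6 to 0.7 points under dependence in the control arm only at log-odds 1 per SD. The correlations, the timing of dropout and the mechanism are all assumptions. This should be fixed before outcome data are seen, because the remedy is cheap and removes a choice from the primary result. It does not invalidate the design or the sample size.

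**What to change.** Make the primary analysis a mixed model for repeated measures on the 4- and 7-month scores, with baseline-by-visit and arm-by-visit terms and an unstructured covariance. Name the 7-month arm contrast as the primary estimate. This model uses every patient in the stated set. Multiple imputation of the 7-month score from the baseline and 4-month scores, followed by the stated regression, is an acceptable alternative; choose one in advance. Keep the 7-month linear regression as a sensitivity analysis and call it complete-case.

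The cost is one paragraph of text. No new data are needed, and Stata 13, the software already named, can fit the model. The downsides are slightly more complex reporting and reliance on missing-at-random, which should be stated.
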